Bone healing at implants installed in sites prepared either with a sonic device or drills. A split-mouth histomorphometric randomized controlled trial.

Brief title: Bone healing at implant installed in sites prepared with either a sonic device or drills

[name], [name], [name], [name], [name] & [name]

[name], [name], [name], ARDEC Academy, Ariminum Odontologica, Rimini, Italy

[name], [name], Department of Medical, Oral and Biotechnological Sciences, University of Chieti-Pescara, Chieti, Italy

[name], Corporación Universitaria Rafael Nuñez, Cartagena de Indias, Colombia

Running Head: sonic device for implant site preparation

Key words: human study, histometry, morphometry, dental implants, bone, bone-to-implant contact, bone density

Corresponding author:

[name], BMBS, PhD, Dentist

[name]

[contact], [contact], E-mail: [contact]

July 17th 2017

Abstract

Purpose: to evaluate histomorphometrically the early healing at implants installed in sites prepared with either a sonic device or conventional drills.

Material and methods: Sixteen volunteer patients will be recruited. Two titanium mini-implants will be installed in the distal segments of the maxilla in recipient sites prepared with either a sonic device or conventional drills. Biopsies containing the mini-implants will be retrieved after 2 weeks in eight patients, and after 6 weeks in the other eight patients. Histomorphometric analyses will be performed.

Key words: Bone-to-implant contact; bone density; dental implants; histometry; histology; sonic device.

INTRODUCTION

A systematic review with meta-analysis compared the use of a piezoelectric device and drills for implant site preparation.¹ Both technical approaches presented similar results regarding implant failure and marginal bone level changes. However, a longer time for site preparation was required for the piezoelectric device compared to the drills. was and operating time.

The healing at implants installed in sites prepared using conventional drills to sites prepared with either a piezoelectric device or a sonic device was studied in animal experiments.^{2,3} No differences in osseointegration were found in both studies. The use of piezoelectric or sonic devices has become widespread during the last years due to the precision offered during the cutting procedures of these devices, the reduced risk of damaging soft tissues, and the clear view of the surgical sites offered by this device during the preparation.⁴⁻⁶

Piezoelectric devices have been largely studied and compared with the use of drills for implant site preparation.^{7,8} In a randomized controlled clinical study,⁹ gain in implant stability was faster in sites prepared with piezosurgery compared to twist drills, while no differences in survival rate were found. As support to this finding, an experimental study in mini pigs,¹⁰ showed that sites prepared with piezosurgery presented a more advanced osteogenesis compared to those prepared with drills.

Comparatively to the piezoelectric devices, lesser amount of clinical¹¹⁻¹⁸ and experimental researches³ have been performed to evaluate the sonic devices. Nevertheless, similar advantages of the piezoelectric instruments are offered by the sonic devices in term of surgical precision, clear view of the surgical field, and low risk of possible damages of the surrounding soft tissues.³ Moreover, the sonic devices have been claimed to produce a similar increase of the temperature during the procedure of that produced by drills, and lower than that produced by piezoelectric instruments.¹⁹

Experimental histological data comparing sonic devices and conventional drills are still scares and histological data from human are not available. Hence, the aim of the present study will be to evaluate histomorphometrically the early healing at implants installed in sites prepared with either a sonic device or conventional drills.

The hypothesis will be that the preparation of an implant recipient site using a sonic instrument might produce different osseointegration compared to a conventional site preparation using drills.

MATERIALS & METHODS

Patient selection

In the present split-mouth histomorphometric randomized controlled trial, sixteen patients will be included. The Declaration of Helsinki on medical protocols and ethics will be followed. The protocol has the approval of the Ethical Committee of the Corporación Universitaria Rafael Núñez, Cartagena de Indias, Colombia (protocol #05-2014; 8 October 2014). In the same institution will be performed all treatments. After having exhaustively illustrated the surgical procedures and the possible complications, a written informed consent will be signed by the patients. The study will be reported according to the CONSORT guidelines.

To calculate a suitable sample, data from an animal experiment in dogs performed by the same research group were used.³ In that experiment, implant site preparations was carried out either with a similar sonic device used in the present study or drills, and a difference of 7.3% in bone-to-implant contact was seen in favor of the sonic groups with an n=6. Considering a possible higher variability in humans and possible dropouts, a sample n=8 pairs of subjects is considered sufficient to reject the null hypothesis that this response difference is zero, with a power 0.8 and $\alpha=0.05$, as evaluated using PS Power and Sample Size Calculations, (William D. Dupont and Walton D. Plummer). Two groups of 8

volunteers will be randomly formed and planned for biopsies retrieval after either 2 or 6 weeks of healing.

The patients included in the present study have to satisfy the following inclusion criteria:

- (i) presence of an edentulous atrophic zone in the posterior segment of the maxilla
- (ii) height of the sinus floor ≥ 10 mm
- (iii) ≥ 25 years of age;
- (iv) smoking ≤ 10 cigarettes per day
- (v) good general health
- (vi) no contraindication for oral surgical procedures
- (vii) not being pregnant.

The following exclusion criteria will be adopted:

- (i) presence of systemic disorders
- (ii) chemotherapy or radiotherapy
- (iii) smokers >10 cigarettes per day
- (iv) previous bone augmentation procedures in the same region.

Moreover, caries and periodontal conditions will be evaluated and, if any of these pathologies are present, they will be treated before starting the study.

Device

Titanium screw-shaped mini-implants, 4 mm long and 2.5 mm in diameter and with a ZirTi® surface (Sweden & Martina, Due Carrare, Padua, Italy) will be used. Surface features of the implants were previously reported.²⁰

Randomization and allocation concealment

Each patient will receive two mini-implants, installed in recipient sites prepared in the distal segments of the maxilla either with a sonic device or drills. The two recipient sites will be

selected prior the surgery, while the type of site preparation will be randomly decided. A researcher, neither involved in the selection of the patients nor in the surgical and prosthetic treatment, carried out electronically the randomization (randomization.com). Sealed opaque envelopes will be prepared and opened at the time of surgery and they will report the position of the sonic sites so that the surgeon will be masked about site preparation type until the surgery. The site will be indicated as mesial or distal position if the two sites will be located in the same quadrant of the maxilla, or as right or left if they will be located in opposite quadrants of the maxilla.

Clinical procedures

All surgical procedures will be performed by an expert surgeon. Local anesthesia will be provided and crestal and releasing incisions will be carried out. Full-thickness mucoperiosteal flaps will be elevated, and the alveolar bone exposed. The control sites (Drills) will be prepared with a lanceolate drill (FS 230, Sweden / Martina), with a maximum diameter of 2.3 mm, while the test sites will be prepared with conical diamond inserts of increasing diameter (SFS99.000.014 to SFS99.000.024, Komet-Brasseler-GmbH, Germany) mounted on a sonic-air surgical instrument (Sonosurgery® TKD, Calenzano, Fi - Italy). The dimensions of the final drill and of the final sonic device allowed the preparation of recipient sites of similar dimensions (about 2.3-2.4 mm in the coronal aspect). The mini-implants will be subsequently installed, a cover screw will be placed on the top of the mini-implants, and the flaps will be sutured allowing a fully submerged healing.

Antibiotics (amoxicillin 875 mg/clavulanic acid 125 mg twice a day for 6 days), non-steroidal anti-inflammatory drugs as needed (Ibuprofen 400 mg), and mouth rinses with 0.12% chlorhexidine three times a day for 10 days will be prescribed. The sutures will be removed after 7 days, and the patients will be enrolled in a maintenance recall. Biopsies

including the mini-implants will be retrieved after 2 or 6 weeks of healing, paying attention to keep the implant in an eccentric position within the trephine, to reduce the dimension of the biopsy and maintaining sufficient tissue for analysis, as previously described.²¹

Histological preparation of the biopsies

The biopsies will be washed in saline solution and immediately stored in 10% buffered formalin. The histological process will be performed in the laboratory facilities at the University of Chieti-Pescara, Italy. The biopsies will be not removed from the trephine. They will be dehydrated in an ascending series of alcohol, and subsequently embedded in a glycol-methacrylate resin (Technovit® 7200 VLC; Kulzer, Wehrheim, Germany). Once the polymerization will be finalized, the biopsies will be sectioned following the longitudinal axis of the samples using precision diamond disks, and specimens of about 150 microns of width will be obtained. The specimens will be afterwards ground to about 30 µm of width and stained with acid fuchsine and toluidine blue.

Histomorphometric evaluation

The histomorphometric evaluation will be performed twice by a blinded author, and mean values will be used. A code will be reported on the histological slides so that no indications will be available on the site preparation procedures and period of healing. All histological analyses will be carried out in ARDEC Academy, Italy, using an Eclipse Ci microscope (Nikon Corporation, Tokyo, Japan) connected to a digital video camera (Digital Sight DS-2Mv, Nikon Corporation, Tokyo, Japan). To carry out measurements, the software NIS-Elements D 4.10 (Laboratory Imaging, Nikon Corporation, Tokyo, Japan) will be used. The percentages of newly formed bone (new bone), pre-existing bone (old bone), bone debris/ clot remnants (debris), and marrow spaces (soft tissue) in contact with the implant surface will be evaluated at x200 magnification from the most coronal contact of

bone to the implant surface (B) to the apical extension of osseointegration (A). The total mineralized bone will be calculated as sum of new and old bone.

Morphometric measurements (tissues density) will be performed, identifying the same tissues above indicated plus vessels, in a region included between B and A, and at a distance from the implant surface of about 0.4 mm. For this purpose, a point counting procedure will be used applying a lattice with squares of 50 microns superposed over the histological slides, using a magnification of x200.

The *interception point* for new and pre-existing bone in contact with the implant surface will be calculated and expressed in days of occurrence and bone-to-implant contact percentage, according to Botticelli et al. (2017).²²

Outcomes Measures

Healing after two weeks

Primary outcome: New bone in contact with the implant surface.

Description: The percentages of new bone in contact with the implant surface will be evaluated in the histomorphometric analysis.

Timeframe: After 2 weeks, to evaluate the early healing after surgery.

Secondary outcome: The percentage of total mineralized bone in contact with the implant surface.

Description: The total mineralized bone will be assessed as sum of new and old bone as evaluated in the histomorphometric analysis.

Timeframe: After 2 weeks, to evaluate the early healing after surgery.

Other pre-specified outcomes: pre-existing (old) bone, soft tissues (marrow spaces, Haversian canals, BMUs canals), bone debris/ clot remnants, and vessels.

Description: The percentages of pre-existing (old) bone, soft tissues (marrow spaces, Haversian canals, BMUs canals), bone debris/ clot remnants and vessels in contact with the implant surface will be evaluated in the histomorphometric analysis.

Timeframe: After 2 weeks, to evaluate the early healing after surgery.

Healing after 6 weeks

Primary outcome: New bone in contact with the implant surface.

Description: The percentages of new bone in contact with the implant surface will be evaluated in the histomorphometric analysis.

Timeframe: After 6 weeks, to evaluate the healing prior to load with a prosthesis.

Secondary outcome: The percentage of total mineralized bone in contact with the implant surface.

Description: The total mineralized bone will be assessed as sum of new and old bone as evaluated in the histomorphometric analysis.

Timeframe: After 6 weeks, to evaluate the healing prior to load with a prosthesis.

Other pre-specified outcomes: pre-existing (old) bone, soft tissues (marrow spaces, Haversian canals, BMUs canals), bone debris/ clot remnants, and vessels.

Description: The percentages of pre-existing (old) bone, soft tissues (marrow spaces, Haversian canals, BMUs canals), bone debris/ clot remnants and vessels in contact with the implant surface will be evaluated in the histomorphometric analysis.

Timeframe: After 6 weeks, to evaluate the haling prior to load with a prosthesis.

Data analysis

Mean values and standard deviations as well as 25th, 50th (median), and 75th percentiles will be calculated for each outcome variable. Means, standard deviations and 95% upper and lower confidence interval of the difference between the means of sonic and drill sites

will be calculated for each variable analyzed for both histometric and morphometric analyses.

The primary variable will be newly formed bone (new bone) in contact with the implant surface. Total mineralized bone, calculated as sum of new and old pre-existing bone, in contact with the implant surface will be considered as secondary variable.

A Wilcoxon test will be used to analyze differences between sonic and drill groups for all outcomes. The level of significance will be set at α 0.05.

With an explorative aim, a Mann-Whitney test will be used to analyze the difference in new bone and total mineralized bone between 2 and 6 weeks of healing.

ACKNOWLEDGEMENTS

This study will be economically supported by ARDEC Academy, Ariminum Odontologica Srl, Rimini, Italy.

There are no conflicts of interest with the material presented.

REFERENCES

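### The power of 0.8 with 8 pairs is stated without naming a test and is not given for the planned Wilcoxon test; if it came from a paired t-test, the exact Wilcoxon test has about 0.74

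*Combined protocol and SAP*

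**What the plan says.** In the combined protocol and SAP, Materials & Methods, Patient selection takes its planning effect from a dog experiment in which "a difference of 7.3% in bone-to-implant contact was seen in favor of the sonic groups with an n=6". It continues: "Considering a possible higher variability in humans and possible dropouts", and then that "a sample n=8 pairs of subjects is considered sufficient to reject the null hypothesis that this response difference is zero, with a power 0.8", at alpha 0.05, "as evaluated using PS Power and Sample Size Calculations". The program is named. The test, the SD of the paired differences, the sidedness and the dropout rate are not.

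Data analysis states: "A Wilcoxon test will be used to analyze differences between sonic and drill groups for all outcomes". It adds: "The level of significance will be set at α 0.05". The split-mouth design implies the signed-rank version, and the plan uses the name Mann-Whitney for its unpaired comparison between healing times. Whether the p-value is exact or asymptotic is not stated. New bone in contact with the implant is the primary outcome at both 2 and 6 weeks, with 8 patients (8 pairs) at each.

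**The concern.** The power figure reads like a calculation for a mean paired difference. The only planning input is a difference, and no distribution is given, which a power calculation for a rank test would need. The test that will decide the primary outcome is a rank test. At 8 pairs its null distribution is so coarse that it cannot be run at exactly 0.05. The stated 0.8 may therefore not be the power of the planned test, even at the effect for which it was claimed. At stake is an understated chance of missing the planned difference at each time point or, with one form of the p-value, a type I error slightly above the stated level.

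**Working it through.** **Inputs**
- From the documents: 8 pairs per time point, power 0.8, alpha 0.05, difference 7.3 points.
- Assumed: two-sided testing, because the Introduction's hypothesis is non-directional (sonic preparation "might produce different osseointegration compared to a conventional site preparation using drills"); a paired t-test behind the 0.8; normal paired differences.
- Not given: the SD of the paired differences. The 0.8 therefore cannot be reproduced forward, and the effect is back-solved from it.

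**1. The plan's figure.** For a paired t-test with n pairs and standardised difference δ (mean over SD of the differences), power is P(|T| > t critical), where T is noncentral t with n − 1 df and noncentrality δ√n. Setting this to 0.80 at n = 8, two-sided 0.05, gives δ = 1.156. For 7.3 points the implied SD is 7.3/1.156 = 6.31 points.

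**2. Level of the exact signed-rank test.** Let W be the smaller signed-rank sum. Under the null all 2^8 = 256 sign patterns are equally likely.
- W ≤ 3: the rank sets are {}, {1}, {2}, {3}, {1,2}, so 5 per tail. Level 10/256 = 0.0391.
- W ≤ 4: add {4} and {1,3}, so 7 per tail. Level 14/256 = 0.0547, above 0.05.

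The exact test therefore rejects only at W ≤ 3.

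**3. Power at δ = 1.156** (1,000,000 simulated normal samples). The t-test has 0.800 and the exact Wilcoxon test 0.737, so the chance of a miss is 1 − 0.737 = 0.263 rather than 0.20. A t-test run at level 10/256 has power 0.755. So about 0.800 − 0.755 = 0.045 of the loss comes from the coarse level, and 0.755 − 0.737 = 0.018 from using ranks.

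**4. Asymptotic p-value.** The null mean of W is 8·9/4 = 18 and its variance is 8·9·17/24 = 51.
- Without continuity correction, W = 4 gives z = 14/√51 = 1.960 and p = 0.04995. The test rejects at W ≤ 4, with power 0.80 and true level 0.0547.
- With correction, W = 4 gives z = 13.5/√51 = 1.890 and p = 0.0587. The test rejects only at W ≤ 3, as the exact test does.

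**5. Dropout readings.** Suppose the 0.80 was meant for fewer evaluable pairs:

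| Pairs at which t-test power is 0.80 | δ | Exact rejection rule and level | Exact Wilcoxon power at that number | Exact Wilcoxon power with all 8 pairs |
|---|---|---|---|---|
| 8 | 1.156 | W ≤ 3, 0.039 | 0.74 | 0.74 |
| 7 | 1.273 | W ≤ 2, 0.047 | 0.77 | 0.81 |
| 6 | 1.435 | W = 0, 0.031 | 0.62 | 0.89 |

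The 6-pair figure can be checked by hand. The test rejects only if all six differences share a sign, with probability about Φ(1.4345)^6 = 0.924^6 = 0.62.

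**6. Sensitivity**
- Other shapes with the same SD and δ = 1.156: exact Wilcoxon power is 0.71 (uniform), 0.76 (Laplace) and 0.78 (t with 5 df).
- If the 0.8 came from a z approximation, δ = (1.960 + 0.842)/√8 = 0.991. The t-test then has 0.67 and exact Wilcoxon 0.60.
- At δ = 1.156, 9 pairs give exact Wilcoxon power of 0.806, so the shortfall is worth about one pair per time point.
- For 7.3 points and an assumed SD of 5, 6, 7, 8 or 10, exact Wilcoxon power is 0.90, 0.78, 0.65, 0.53 or 0.37, against 0.94, 0.84, 0.72, 0.60 or 0.43 for the t-test.

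**The case against.** A reader might infer that the trial has power 0.74, or misses the planned difference 26% of the time at each time point. The documents do not support that. The 0.74 is back-solved by fixing t-test power at 0.80 with 8 pairs. Without an SD the trial's actual power is unknown, and the assumed SDs above move it from 0.90 to 0.37, far more than the choice of test does. The 7.3% is also bone-to-implant contact in dogs, while the primary outcome is new bone in contact in humans.

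Two further points favour the plan. First, the 8 already contains an allowance of unknown size for dropout and variability. If the 0.8 was meant for 7 or 6 pairs and nobody is lost, the exact test reaches 0.81 or 0.89 and there is no shortfall. Second, the exact p-value is itself an assumption, and an uncorrected asymptotic p-value shows no power loss at 8 pairs. Nor is the Wilcoxon test a poor choice: it is a valid paired test.

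These points make the 0.74 conditional, but they do not tie the 0.8 to the planned test. The asymptotic version reaches 0.80 only at a true level above the stated 0.05. The dropout reading gives 0.77 or 0.62 at the number of pairs it would have been sized for. The comparison between tests does not depend on the missing SD: exact Wilcoxon power lies below t-test power at every SD tried.

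**Conclusion.** The point holds in a conditional and modest form. The plan states power 0.8 without naming a test and gives no power for the Wilcoxon test that decides the primary outcome. Under three assumptions (a two-sided paired t-test with 0.80 power at 8 pairs, normal differences, and an exact or continuity-corrected p-value), power is about 0.74, a loss of about 6 percentage points. Without those assumptions the size changes: it can be larger (0.60 under a z approximation), absent (all pairs kept after a dropout allowance), or appear as a true level of 0.0547 instead of a power loss. What stands on every reading is that the power statement does not identify its test, and that at 8 pairs the unspecified form of the p-value alone decides whether W = 4 is significant. The missing SD is the larger gap, and filling it is part of the same correction.

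**What to change.** In Data analysis, specify the exact two-sided Wilcoxon signed-rank test for the sonic-versus-drill comparisons. In Patient selection, name the test behind the 0.8 and state the SD of the paired differences, the sidedness and the dropout allowance. Then restate the power for the exact test: about 0.74 at 8 pairs if the inputs prove to be a two-sided paired t-test at 8 pairs with normal differences, and otherwise the value recomputed from the inputs actually used.

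This costs a few sentences and no extra patients. The downside is that the stated power may be slightly less favourable.

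Optional, and not needed to correct the figure: make an exact sign-flip permutation test on the mean paired difference the primary test, with the Wilcoxon test kept as a sensitivity analysis. Under the same assumptions its power is about 0.78, and it fits the mean differences and confidence intervals already planned. It is somewhat more sensitive to one extreme pair.

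### Does it matter that the planned 95% interval is for a difference in means while significance comes from a Wilcoxon test?

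*Combined protocol and SAP*

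**What the plan says.** The Data analysis section first lists summary statistics. For each outcome variable there are means, standard deviations and quartiles, and then, for both the contact and the density measurements, "Means, standard deviations and 95% upper and lower confidence interval of the difference between the means of sonic and drill sites". The section does not say how the interval is computed, whether it is paired, or that it is descriptive.

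Two paragraphs later it names the test: "A Wilcoxon test will be used to analyze differences between sonic and drill groups for all outcomes". The next sentence fixes alpha: "The level of significance will be set at α 0.05". Sidedness is not stated, but the hypothesis in the Introduction is non-directional: sonic preparation "might produce different osseointegration compared to a conventional site preparation using drills". For the comparison of healing periods, which involves different patients, the plan names another procedure: "a Mann-Whitney test will be used to analyze the difference in new bone and total mineralized bone between 2 and 6 weeks of healing".

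The Patient selection section sizes the trial in pairs: "a sample n=8 pairs of subjects is considered sufficient to reject the null hypothesis that this response difference is zero, with a power 0.8". Its planning figure comes from a dog experiment, where "a difference of 7.3% in bone-to-implant contact was seen in favor of the sonic groups with an n=6". The section on randomization gives each patient one sonic and one drill site. Eight patients are biopsied at 2 weeks and the other eight at 6 weeks, so each comparison has 8 pairs.

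**The concern.** A confidence interval and a test that sit side by side in a results table are usually read as one statement. Here they are not. The interval concerns a mean, the test is rank-based, and neither is obtained from the other. With only 8 pairs the exact signed-rank p-value moves in coarse steps around 0.05, whereas a t-based interval has no such steps. A reader could therefore meet a primary-outcome interval that excludes zero beside a non-significant test, or the reverse, and the plan has no sentence on how to present that. There are also many opportunities: six contact outcomes at two time points make 12 comparisons before the density measures are counted. If the authors then stressed whichever result looked better, the stated error rate would no longer describe the conclusions.

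**Working it through.** **Inputs.** From the documents: 8 pairs per comparison, alpha 0.05, power 0.8, planning difference 7.3. Assumed, because not stated: two-sided test, signed-rank form with exact p-value, paired-t interval, no ties or zeros, and the SD and shape of the within-patient differences.

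**The plan's own figure.** The 8 pairs cannot be reproduced, since no SD is given. Solving backwards with a two-sided paired t-test, 8 pairs give 80% power for 7.3 if the SD of the differences is about 6.3 (standardized difference 7.3/6.315 = 1.156). With SD 10 the power is 43%. These SDs serve only as a range for what follows.

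**Steps of the exact test.** Eight differences have 2^8 = 256 equally likely sign patterns under the null. The numbers of patterns with rank sum 0, 1, 2, 3, 4, 5 are 1, 1, 1, 2, 2, 3, so:

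- W = 3: p = 2 × 5/256 = 0.0391
- W = 4: p = 2 × 7/256 = 0.0547
- W = 5: p = 2 × 10/256 = 0.0781

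The test therefore has size 3.9%. A 95% paired-t interval excludes zero in 5.0% of null samples under normality.

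**How often they disagree.** Simulation, 300,000 samples of 8 normal differences per row:

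| Standardized difference | Interval excludes 0 | Test significant | Interval only | Test only | Total disagreement |
|---|---|---|---|---|---|
| 0 | 4.99% | 3.89% | 1.41% | 0.30% | 1.71% |
| 0.5 | 23.28% | 19.27% | 4.84% | 0.83% | 5.67% |
| 0.9 (SD 7.3/0.9 = 8.1) | 59.16% | 52.06% | 8.12% | 1.02% | 9.14% |
| 1.155 (SD 7.3/1.155 = 6.3) | 79.94% | 73.60% | 7.10% | 0.76% | 7.86% |

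At a difference of 7.3 with SD 10 the total is 8.3%. Of the normal-data cases where only the interval excludes zero, about 92% have W = 4 or 5, that is p = 0.055 or 0.078. With the asymptotic test without continuity correction, the totals at SD 6.34, 8 and 10 fall to 4.9%, 6.2% and 6.0%.

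Over the 12 contact comparisons the expected number of disagreements is about 12 × 0.017 = 0.2 with no effects and 12 × 0.09 = 1.1 if every comparison had a difference of the planning size.

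**Outside normality.** In the scenarios tried, total disagreement reached 8.0% with heavy tails (t with 3 df) and 14.4% with skewed differences (shifted lognormal). Two constructed data sets show both directions:

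- 10, 9, 8.5, 8, 7.5, 7, 6.5, −7.6: mean 48.9/8 = 6.11, interval 1.39 to 10.84; the negative value has rank 4, so p = 0.0547.
- 1, 2, 3, 4, 5, 6, 7, 40: mean 68/8 = 8.5, interval −2.27 to 19.27; W = 0, so p = 2/256 = 0.0078.

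**Would a matched interval be a clear gain?** The Hodges-Lehmann interval from the 4th smallest to the 4th largest of the 36 Walsh averages has coverage 1 − 10/256 = 96.1%, and it agreed with the exact test in every simulated sample. It is about 1.095 times as wide as the paired-t interval under normality, and it assumes symmetric differences. Agreement is also not guaranteed once zeros occur. For 0, −2, 1.5, 3, 4.2, 5.3, 6.4, 7.7, dropping the zero leaves 7 pairs with W = 2 and p = 2 × 3/128 = 0.047. The four smallest Walsh averages of all eight are −2, −1, −0.25 and 0, so the lower limit is exactly 0 and the interval does not exclude zero.

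**The case for a change.** The best case for a change is that it costs one sentence. The mismatch is real, it can affect the primary outcome, and at a difference of the planning size it would appear in roughly one comparison in twelve. The plan never calls the interval descriptive and never says it comes from within-patient differences. A Hodges-Lehmann interval is standard for a signed-rank test and removes the conflict for continuous data.

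The arithmetic stands, and so does the observation that conflict is not confined to borderline p-values when data are skewed. Three parts do not carry through.

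- A rule does exist. The Wilcoxon test is the only sonic versus drill test named, and the significance level follows it directly. If the two differ, the Wilcoxon result is the significance result.
- Pairing is not in real doubt. The split-mouth design, the sample size in pairs and the separate unpaired test for healing time all point the same way.
- Replacing the mean difference is a trade-off. The mean keeps the scale of the 7.3 planning figure and answers a question that readers ask. The alternative is wider, assumes symmetry, and needs its own rule for zeros, which are conceivable for minor tissues such as debris or vessels.

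**Conclusion.** The mismatch exists but does not call for a change to the plan. Followed as written, the plan gives a sound result: one test decides significance, its exact size with 8 pairs is 3.9%, and a mean difference with its interval is reported beside it. Disagreement would be expected in about 2% of comparisons with no effect and up to about 9% at the planning difference. These figures rest on normal differences, a paired-t interval, an exact two-sided signed-rank test and SDs of 6.3 to 10, none of which the documents state. The planning difference itself is a dog bone-to-implant contact figure, not human new bone, which is the primary variable. With skewed differences the rate reached about 14% in the scenarios tried. None of this alters the error rate of the stated decision. The missing words, that the interval is paired and descriptive, are ones a competent analyst would supply from the design when reporting.

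### Does testing new bone as primary at both 2 and 6 weeks, each at 0.05, need a multiplicity adjustment?

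*Combined protocol and SAP*

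**What the plan says.** The Introduction gives one non-directional hypothesis: sonic preparation "might produce different osseointegration compared to a conventional site preparation using drills". It names no healing time.

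Under Patient selection, 8 pairs are judged enough for power 0.8 at a level of 0.05, based on a 7.3% difference in bone-to-implant contact in dogs. Two groups of that size are then planned: they "volunteers will be randomly formed and planned for biopsies retrieval after either 2 or 6 weeks of healing". The Abstract confirms that the 2-week and 6-week biopsies come from different patients.

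Outcomes Measures has a separate block for each period, each with its own primary, secondary and other outcomes. New bone contact is primary in both. The purposes differ: "Timeframe: After 2 weeks, to evaluate the early healing after surgery" and "Timeframe: After 6 weeks, to evaluate the healing prior to load with a prosthesis".

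Data analysis states "The primary variable will be newly formed bone (new bone) in contact with the implant surface", without a time point. It continues "A Wilcoxon test will be used to analyze differences between sonic and drill groups for all outcomes" and "The level of significance will be set at α 0.05". Only the comparison of 2 with 6 weeks, by a Mann-Whitney test, is called explorative.

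**The concern.** With one hypothesis, two primary tests and one significance level, the plan appears to offer two chances of success. It gives no testing order, no split of the 0.05, and no rule for reading a result that is positive at one time and negative at the other. If the investigators could count whichever time point came out positive, 0.05 would understate the error of the overall claim, and the reading could be chosen after the data were seen.

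There is a smaller, related gap. The plan does not say whether the Wilcoxon p-value is exact or approximate. With 8 pairs that can decide a borderline result: a rank sum of 4 is not significant by the exact test but falls just under 0.05 by one version of the normal approximation.

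**Working it through.** **Inputs.** From the plan: 8 pairs per group, different patients in each group, level 0.05, difference 7.3 points, power 0.8. Assumed: the paired signed-rank test (the design is split-mouth, and the unpaired Mann-Whitney test is named separately), two-sided (the hypothesis has no direction), no ties or zero differences.

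**The plan's own figure.** No standard deviation is given, so 8 pairs cannot be reproduced forwards. Working backwards with a two-sided paired t-test, 80% power at 8 pairs needs a standardised difference of 1.156, so the SD of the paired differences is 7.3 / 1.156 = 6.31 points. The planned 8 pairs are assigned to each healing group, not shared between them.

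**Error of one test.** With 8 pairs there are 2^8 = 256 equally likely sign patterns under the null. The numbers giving a smaller rank sum W of 0, 1, 2, 3 and 4 are 1, 1, 1, 2 and 2.

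- W ≤ 3: 2 × 5/256 = 0.0391, the largest exact size not above 0.05.
- W ≤ 4: 2 × 7/256 = 0.0547.

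With 7 pairs the exact size is 2 × 3/128 = 0.0469. With 6 it is 2 × 1/64 = 0.0313.

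**Error over two tests.** The groups share no patients, so the tests are independent. If either result is enough, the error is 1 − (1 − a₁)(1 − a₂).

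| Pairs | Each test | Either test |
|---|---|---|
| 8 and 8 | 0.0391, 0.0391 | 0.0766 |
| 8 and 7 | 0.0391, 0.0469 | 0.0841 |
| 7 and 7 | 0.0469, 0.0469 | 0.0916 |
| 8 and 6 | 0.0391, 0.0313 | 0.0691 |
| 6 and 6 | 0.0313, 0.0313 | 0.0615 |

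At the nominal level the figure would be 1 − 0.95² = 0.0975. If both results were required, it would be 0.0391² = 0.0015. If each is its own claim, the middle column applies, and every entry is below 0.05.

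**Exact or approximate.** At 8 pairs the mean of W is 18 and its variance 51. For W = 4, z = (4 − 18)/√51 = −1.960, so p = 0.04995 without continuity correction and 0.0587 with it. The corrected version therefore agrees with the exact test. Only the uncorrected version differs, with size 0.0547 per test and 1 − (1 − 0.0547)² = 0.1064 for either. With fewer pairs the choice can work in both directions. W = 1 at 6 pairs is 0.0625 exact against 0.0464 uncorrected. W = 2 at 7 pairs is 0.0469 exact against 0.0519 corrected.

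**What an adjustment would cost.** Holm would test the smaller p-value against 0.025. The exact size at 8 pairs is then 6/256 = 0.0234, and the error over both tests is 1 − (1 − 0.0234)² = 0.0463. Simulated power per time point with exact tests, normal differences, a true difference of 7.3 and 8 pairs in each group:

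| Assumed SD | Unadjusted | Holm, effect at both times | Holm, effect at one time |
|---|---|---|---|
| 6.31 | 73.7% | 69.4% | 62.5% |
| 8 | 53.2% | 46.5% | 41.9% |
| 10 | 36.8% | 29.7% | 27.4% |

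A group reduced to 6 pairs could not pass Holm's first step at all, because its smallest exact p-value is 0.031. Under a fixed sequence the first test is unaffected, but power for the second falls from 73.7% to 54.3% at SD 6.31.

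**The case for a change.** The strongest case for a change is that the plan never says which reading applies. One hypothesis and one primary variable without a time point suggest a single claim, and both sonic-versus-drill primaries stand outside the explorative label. The plan also foresees losses ("Considering a possible higher variability in humans and possible dropouts"), and with 7 pairs in each group the either-result error reaches 9.2%. One sentence written in advance would close the question, while the same sentence written afterwards would carry less weight.

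Part of this stands. The hypothesis is loosely worded, and one hypothesis per time point would read better. But that sentence would most naturally confirm two separate comparisons at 0.05, which leaves every test as it is. The either-result rule behind 7.7% and 9.2% is not in the document. Both time points are named as primary beforehand, so a report that follows the plan shows both results, and a reader can see when only one is positive.

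On the p-value, the exact signed-rank test is the sensible choice at 8 pairs, and nothing in the plan points to the uncorrected approximation on which the 10.6% depends.

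**Conclusion.** No change is needed. The 7.7% is correct arithmetic, but it belongs to a decision rule that the plan does not adopt. The full sample size in each group, the separate patients, the stated purposes and the separate outcome lists all describe two parallel comparisons. Each has one primary test at 0.05, and its exact error is 3.9% at 8 pairs and at most 4.7% with 6 or 7.

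Whether independent groups answering related questions should share one 0.05 is a matter on which statisticians differ. Sharing it would cost roughly 4 to 11 percentage points of power per time point (73.7% to 69.4% or 62.5%) at the SD implied by the plan's own sample size. Leaving the tests unadjusted is a fair trade-off. The unstated p-value method is a gap that analysts would fill sensibly with the exact test.

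The error rates assume two-sided exact signed-rank tests without ties or zeros. The power figures also rest on SDs that the plan does not give, and on a dog difference in bone-to-implant contact standing in for new bone.
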